7.4. Statistical Methods

In addition to the analyses described subsequently, descriptive statistics will be used during the course of the study as part of data management procedures for monitoring data quality. A brief overview of some of the statistical methods that may be used at the time of analysis, both for descriptive purposes and in more comprehensive analysis of the primary research questions, is summarized in the following sections. It is recognized that these methods may be revised and additional ones considered as the details of the specific analyses are developed.

7.4.1. Descriptive Analyses and Primary Efficacy and Safety Analyses

Standard descriptive statistics will be used to summarize baseline characteristics and study outcome measures at each follow-up visit, both overall, and within each treatment group.

Examination of baseline characteristics will include estimates of the distribution of age, race, and other demographic characteristics, lab measures and study center. Summary statistics such as means, medians, and ranges will be produced for all measured variables.

Frequencies will be computed for all categorical and ordinal variables. Graphical methods including stem-and-leaf diagrams and boxplots will be used to examine distributions, identify potential influential points, and guide in the choice of transformations, if warranted. The balance of baseline measures across the three treatment groups will be compared using appropriate k-sample tests, including Kruskal-Wallis tests and Fisher's exact tests.

Analysis of Primary Efficacy and Safety Outcomes Mean (\pm standard deviation) or median (interquartile values) of baseline and end of study measurement in the primary endpoint E' will be presented. Change in E' velocity at 36 weeks will be assessed and reported quantitatively, and descriptive statistics for absolute and % change will be provided. Mixed effects linear regression models with baseline covariate adjustments will be used for assessment of treatment effects. Model assumptions regarding homoscedasticity and normality will be examined using standard techniques.

For the primary safety endpoint, tables with percent incidence and incidence rate (for events that can occur more than once during follow-up) will be prepared. Differences in incidence and incidence-rate will be assessed using logistic regression or Poisson regression with factors for assigned treatment and the stratification variable. In particular, for safety endpoints, we will investigate the potential change in potassium level in placebo and treatment groups with monthly measure of potassium. Mixed effects linear regression models will be used to assess the direction and time averaged magnitude of change in potassium, with and without controlling for baseline covariates. The proportion of serious hyperkalemia in treatment and placebo groups will be compared with Chi-square test or Fisher's exact test.

The primary analysis will examine the intention to treat population. All analyses will be repeated in the as-treated, all-treated and per-protocol populations (see **Section 7.3**). Secondary endpoint analyses will be presented using analogous techniques. $P < 0.05$ will be considered

significant in all analyses.

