NIDDK	National Institute of Diabetes and Digestive and Kidney Diseases
OHRP	Office of Human Research Protections
PET	positron emission tomography
PHI	protected health information
PICP	procollagen type I carboxy-terminal peptide
PTH	parathyroid hormone
QD	daily
RCT	randomized controlled trial
SAE	serious adverse event
SAP	statistical analysis plan
SBP	systolic blood pressure
SPL	spironolactone
TDI	tissue Doppler index
UAE	unanticipated adverse event

Study Summary

Title	Safety and Cardiovascular Efficacy of Spironolactone in Dialysis-Dependent ESRD Trial
Short Title	SPin-D Trial
NCT Identifier	NCT02285920
Phase	Phase II
Methodology	Randomized, double-blind, placebo-controlled 4-arm
Study Duration	2 years
Study Center(s)	Brigham and Women's Hospital George Washington University University of Washington Vanderbilt University / Nashville VA Medical Center University of Pennsylvania (Data Coordinating Center)
Objectives	
 • To generate pilot data on the safety and tolerability of spironolactone (SPL) in patients with dialysis-dependent ESRD. • To generate pilot estimates of the effect of SPL compared with placebo on cardiovascular efficacy parameters in patients with dialysis-dependent ESRD.
Number of Participants	125
Diagnosis and Main Inclusion Criteria	Dialysis-dependent ESRD
Study Product, Dose, Route, Regimen	Spironolactone 12.5, 25, or 50 mg, orally daily
Duration of administration	36 weeks
Reference therapy	Placebo
Major Outcomes	
 • Safety: hyperkalemia, hypotension • Tolerability: treatment adherence • Efficacy: change in mitral annular E' velocity • Feasibility: recruitment
Statistical Methodology	
Mixed effects linear regression models will be used to assess the direction and time averaged magnitude of change in efficacy parameters, with and without controlling for baseline covariates, to compare the effects of therapy.
 
These mixed effects models will also be utilized to investigate the potential shift in overall potassium levels. The incidence of safety events, especially serious hyperkalemia, in treatment and placebo groups will be compared with Chi-square test or Fisher's exact test.

CONFIDENTIAL

Do not disclose or use except as authorized by the Hemodialysis Novel Therapies Consortium.

1. Introduction

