6.3. Baseline/Randomization Visit (Day 0)

The Baseline/Randomization visit will take place on a non-dialysis day during the short (approximately 44-hour) inter-dialytic interval. At this visit, medication use, vital signs, a brief physical examination and adverse events will be recorded, and eligibility will be confirmed. Once eligibility has been confirmed, randomization to treatment group will be performed through the centralized Data Management System.

Serum and plasma will be collected, aliquoted, and shipped for batched measurement of cardiac and inflammatory markers and for long-term storage. Whole blood will be collected for DNA extraction. Blood will also be drawn for local measurement of chemistries and complete blood count. If blood cannot be collected on the day of the Baseline/Randomization visit (Day 0), it should be collected the following day prior to the dialysis session and before the initiation of study drug. If blood for batched analyses, long-term storage, and DNA extraction cannot be obtained on the day of randomization or the following day, it is acceptable to obtain the blood within the 10 days prior to the Baseline/Randomization visit, and, if on a dialysis day, prior to initiation of the dialysis session. However, the blood for local measurement of chemistries and

complete blood count will be obtained on the day of or the day after the Baseline/Randomization visit rather than within 10 days prior.

Tissue Doppler Index echocardiography (TDI echo) will be performed on the day of the Baseline/Randomization visit. If the TDI echo cannot be performed at that visit (Day 0), it should be completed as soon as possible thereafter and within 7 days after the Baseline/Randomization visit. The echo must be performed on a non-dialysis day during the short (approximately 44 hour) inter-dialytic interval. A subset of participants will have positron emission tomography (PET scan) (after exclusion of pregnancy).

A 2-week supply of study drug will be dispensed and the participant will be instructed to start the study drug the following day, after dialysis.

6.4. Week 1, Week 2, Week 3, Week 4, Week 5, and Week 6 Visits (window for each: -4 to +3 days)

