6.6. Week 36 Visit (End of Treatment) (-7 to +7 days)

At the Week 36 visit, participants will be interviewed in person to review the occurrence of adverse events as described in **Section 6.4**. Dialysis unit records will be reviewed for inter-current laboratory values, the occurrence of hypotension, and changes to the dialysis prescription. Pill containers will be returned and unused pills counted and destroyed. Serum and plasma will be collected, aliquoted, and shipped for batched measurement of cardiac and inflammatory markers and for long-term storage. Blood will also be drawn for local measurement of chemistries, complete blood count and, for women of childbearing potential, serum pregnancy testing. If the blood collection is performed on a dialysis day, the collection should take place prior to the dialysis session. End-of- study TDI echo will be performed and a subset of participants will have a PET scan performed (following exclusion of pregnancy).

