7.1. Sample Size Determination

Sample size considerations were framed using standard study design parameters to ensure 80% power to detect pre-specified effect sizes utilizing intermediate outcomes. However, for this early phase pilot study, the primary focus is directed at assessing safety and feasibility, with no attempt to create critical test result regions for standard hypothesis testing.

From preliminary studies, we assumed estimated baseline parameters of E' to be 5.8 ± 1.8 cm/s.^{34, 43, 87, 88} Assuming a correlation ≥ 0.2 between pre and post-therapy E' , and a 10% dropout rate of study participants by the end of the study, a sample size of 125 (2:3; 50 patients for the placebo arm and 25 per SPL dose x 3 active treatment arms) will provide 80% power to detect effect size of 0.7SD (1.3 cm/sec) difference in change from baseline to 9 month endpoint in E' , equivalent to a 22% average reduction across the 3 active SPL treatment arms. Short-term studies with SPL in diabetes were consistent with an effect of this magnitude⁵⁴.

For the safety endpoint of hyperkalemia incidence, we assumed a 5% incidence in the placebo arm. With a sample size of 125, derived under the effect size considerations noted previously, this design provides 80% power to detect an average incidence of 22% across the 3 SPL dose arms. Moreover, this same sample size also provides 80% power to detect a small difference of 0.1 mEq/L in time-averaged serum potassium concentration, treated as a continuous variable, between placebo and treatment arms.

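### Does the unnamed covariate list for the primary E' model put the efficacy analysis at risk?

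*Combined protocol and SAP*

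**What the plan says.** - Section 7.4.1 gives the E' analysis one modelling sentence: "Mixed effects linear regression models with baseline covariate adjustments will be used for assessment of treatment effects". It names neither baseline E' nor the randomization strata. The safety regressions in the same section do carry a stratification term.
- The Statistical Methodology entry in the Study Summary describes mixed models of change in efficacy parameters, "with and without controlling for baseline covariates, to compare the effects of therapy". It does not say which version leads. Similar wording in Section 7.4.1 concerns potassium, not E'.
- Section 7.4 calls the methods an overview and adds: "It is recognized that these methods may be revised and additional ones considered".
- Section 7.1 sizes the trial on a "difference in change from baseline to 9 month endpoint in" E', with SD 1.8 cm/s, 10% dropout, 50 placebo and 75 spironolactone participants, and a correlation stated as "Assuming a correlation ≥ 0.2 between pre and post-therapy" E'.
- Section 6.3 schedules the baseline echo on Day 0. If that fails, "it should be completed as soon as possible thereafter and within 7 days after the Baseline/Randomization visit". On drug start it says "the participant will be instructed to start the study drug the following day, after dialysis".
- Section 6.6 has the second echo at Week 36 ("study TDI echo will be performed"). Section 6.6.1 moves the final assessments to an Early Withdrawal visit for participants who leave before then.

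**The concern.** With one echo before treatment and one after, the choice of model matters. An unadjusted change score gives the same treatment contrast as a two-time-point mixed model whose baseline means are free to differ by arm. Both carry chance baseline imbalance in E' into the estimate. Both have larger variance than a model with baseline E' as a covariate. The Study Summary could be read as allowing either analysis, and the power calculation is framed on change. A reader may therefore worry that the main efficacy estimate will come from the weaker version, or that two versions will disagree with nothing to say which counts. The loss would be greatest in the comparisons of a single dose with placebo.

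A second worry is that a deferred baseline echo can fall after the first doses of study drug. A change score would subtract any early drug effect in full. A baseline-adjusted model would subtract only r times that effect.

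**Working it through.** **Inputs.** From Section 7.1: SD 1.8 cm/s; r at least 0.2; 10% dropout, leaving 45 placebo and 67.5 pooled spironolactone completers (22.5 per dose); effect 0.7 SD = 0.7 × 1.8 = 1.26 cm/s, printed as 1.3. Section 7.4.1 sets P < 0.05, taken here as two-sided. Assumed: equal SD at both echoes, a common r in all arms, a normal approximation. The documents give only the lower limit for r; 0.5 and 0.7 are illustrations.

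**The plan's own figure.** SD of change = 1.8 × √(2(1 - 0.2)) = 2.277. Standard error = 2.277 × √(1/45 + 1/67.5) = 2.277 × 0.1925 = 0.438. Then 1.26/0.438 = 2.88, and power = Φ(2.88 - 1.96) = 82% (84% at 1.3 cm/s). Solving for sample size gives 107.5 completers, or 120 after dividing by 0.9, against 125 planned. The stated 80% therefore holds for an unadjusted change score.

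**Effect of adjusting for baseline E'.** The variance is 2(1 - r)SD² for change and (1 - r²)SD² with baseline E' as a covariate. The ratio is (1 - r²)/(2(1 - r)) = (1 + r)/2, so the saving is (1 - r)/2. A simulation of 20,000 trials at r = 0.2 gave a saving of 40.4%.

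| r | SD, change | SD, adjusted | Variance saving | Pooled power, change / adjusted | Pooled difference detectable at 80% power, change / adjusted (cm/s) |
|---|---|---|---|---|---|
| 0.2 | 2.277 | 1.764 | 40% | 82% / 96% | 1.23 / 0.95 |
| 0.5 | 1.800 | 1.559 | 25% | 95% / 99% | 0.97 / 0.84 |
| 0.7 | 1.394 | 1.285 | 15% | above 99% / above 99% | 0.75 / 0.69 |

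For one dose against placebo (45 vs 22.5, no multiplicity adjustment), power for change against adjusted is 57% vs 79%, 77% vs 88% and 94% vs 97% at the same values of r.

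**Adding the strata.** Site, vintage and ACEI/ARB use take 3 + 1 + 1 = 5 degrees of freedom, and baseline E' takes 1, out of about 108. If the strata are unrelated to E', simulation puts the variance ratio to the change score at 0.625, 0.794 and 0.893. The net saving is then about 37%, 21% and 11%.

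**When the saving is zero.** If baseline E' is already among the adjustments that Section 7.4.1 promises, there is nothing left to gain. A mixed model with both echoes as responses and a common baseline mean has the same efficiency.

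**Deferred baseline echoes.** If a share p of echoes is deferred and a fraction f of the Week 36 effect is already present, a change score loses p × f of the effect and the adjusted model loses r × p × f. The documents give neither p nor f. On a thrice-weekly schedule (assumed), a deferred echo follows 1 to 6 doses, all at the common starting dose. If the effect built up evenly over 36 weeks (an assumption), six days would be 6/252 = 2.4% of it. The change score could then lose no more than 2.4% even if every baseline echo were deferred that long. A faster early response would raise this figure.

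**The case for a change.** The best case for a change is that it would cost a sentence and no data. Section 2.1 sets out to test a hypothesis on E', and Section 7.4.1 applies P < 0.05 to all analyses, so pilot status does not fully excuse an open primary model. Section 7.3 calls dose-related efficacy a primary question, and the single-dose comparisons are where precision is scarcest.

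Part of this stands. No section names the E' covariates, and none ranks the adjusted and unadjusted versions.

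The rest carries less weight:

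- The section that governs the analysis specifies adjustment. The unadjusted option for efficacy appears only in a summary sentence covering efficacy parameters generally. The natural reading is that the adjusted model leads and the unadjusted one supports it.
- Inflated false-positive error would need a rule of claiming success if either version reached significance. The plan has no such rule, and Section 7.1 disclaims critical regions for hypothesis testing.
- Section 7.1 powers the average of the three dose arms, not each dose. The sentence in Section 7.3 introduces the as-treated supplement, which uses mean dose received for efficacy.
- Replacing the mixed model with a regression of Week 36 E' on baseline is not a clear gain. It would drop anyone missing either echo, although Section 7.3 wants all available data and methods robust to missingness. It would also leave open how Early Withdrawal echoes are used. That is a trade-off between reasonable models.
- The deferred-echo point supports at most a sensitivity analysis.

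**Conclusion.** No change to the plan is needed. The covariate list is a real but minor omission. An analyst following Section 7.4.1 would adjust for baseline E', and adding the randomization strata would be routine. In that case the loss is zero. In the worst reading, an unadjusted change score at the planning lower limit r = 0.2, the variance is 2.277²/1.764² = 1.67 times what it could be (a 40% saving forgone). Pooled power is then 82% instead of 96%, still above the 80% the plan claims. At higher correlations the difference shrinks quickly.

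The sample size stands, and the unadjusted estimate would be unbiased under randomization, apart from any small early drug effect in deferred baseline echoes. What could be lost is some precision in pilot estimates, in a trial whose stated focus is safety and feasibility. These figures rest on SD 1.8 cm/s at both echoes, a common correlation across arms, 10% dropout and a two-sided 5% level. The values r = 0.5 and 0.7 are illustrations, not planning inputs.

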3.2. Study Endpoints

3.2.1. Primary Endpoints

Safety

The primary safety endpoints are:

- 1) The incidence of serum potassium >6.5 mEq/L
- 2) The incidence of serious hypotension defined as hypotension requiring hospitalization or treatment in an emergency room and not attributable to overt sepsis, acute myocardial infarction, or other cardiovascular event (e.g. aortic dissection).

Tolerability

Tolerability will be assessed on the basis of whether participants can continue the assigned dose throughout the entire treatment period. Any reduction in dose of study medication will be considered a failure of primary tolerability.

Efficacy

The primary efficacy parameters will be measured between baseline and 36 weeks: Change in mitral annular E' velocity will be measured using Tissue Doppler Index (TDI) echocardiography of the left ventricle as a measure of diastolic function and as surrogate measure of left ventricular fibrosis.

E' has been chosen to be the primary echocardiographic endpoint because the intra-observer coefficient of variation is low⁷¹ and multiple studies demonstrate a high correlation with myocardial fibrosis⁷²⁻⁷⁴, a primary biologic endpoint of interest. E', for example, parallels the accumulation of myocardial collagen and fibrosis in the senescence prone mouse⁷⁵, and correlates with endomyocardial fibrosis after human cardiac transplant⁷⁶ as well as the presence of late gadolinium enhancement⁷⁷ – a highly-validated measure of myocardial scar – across multiple disease states. Furthermore, abnormalities in TDI have been strongly linked to mortality in multiple disease states⁷⁸⁻⁸⁰ demonstrating that TDI is a clinically relevant measure. In addition, ESRD-specific studies show that E' is highly correlated with LV mass and other indices of diastolic function, and that changes in E' predict mortality^{34, 81}.

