5.3. Method for Assigning Participants to Treatment Groups

The DCC will generate randomization schedules stratified by 1) participating recruitment site; 2) dialysis vintage (≥ 1 vs. < 1 year on dialysis) and 3) angiotensin converting enzyme inhibitor (ACEI) or angiotensin receptor blocker (ARB) use. Randomly permuted blocks of random sizes will be used to control the balance of participants assigned to each treatment regimen within each stratum. This method guarantees that at no time during randomization will the number of participants in any arm be grossly imbalanced, and ensures that the sites will be unable to predict assignments. Both longer dialysis vintage and use of ACEI or ARB increase the likelihood of hyperkalemia through loss of residual renal function and drug effects, respectively, and thus, are potential confounders that should be balanced across treatment groups.

All randomization schedules will remain confidential, and known only to authorized members of the DCC staff and the central pharmacy.

All relevant screening and eligibility confirmation data will be entered into the centralized data management system in advance of randomization in order for an eligible participant to be randomized. When the study team agrees that the patient should be randomized, and the "Ready to Randomize Report" confirms that all eligibility criteria have been met, the Study Coordinator will implement the web-based randomization assignment managed centrally at the DCC. This centralized randomization process will provide a randomized treatment assignment for that participant within the relevant stratum, linked with a specific study drug kit prepared at the central pharmacy. This kit will be provided to the local investigative team for distribution at the randomization/baseline visit.

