6.2. Screening Visit (Day –30 to Day 0)

Potential participants expressing interest in enrolling in the study will be scheduled for a Screening visit. This visit may take place at the local dialysis unit or at the Clinical Center and may take place over more than 1 visit. Screening activities must be completed within 30 days prior to the baseline visit.

Informed consent will be obtained and documented before any study procedures are performed. Demographic data (age, sex, race), medical history (hypertension, coronary artery disease, coronary revascularization, diabetes, hypercholesterolemia, cerebral or peripheral vascular disease, peptic ulcer disease, cancer, smoking, arrhythmia, cause of ESRD, dialysis vintage,

prior transplant), dialysis unit labs (chemistries, intact parathyroid hormone, complete blood count), and dialysis prescription will be collected during Screening. Blood will be drawn for serum pregnancy testing in women of childbearing potential. Participants will perform an inter-dialytic urine collection prior to or within seven days following the baseline visit, for assessment of residual renal function. The urine collection will begin immediately after dialysis and continue until the start of the next dialysis session, and will be performed during one of the 44-hour (approximately) inter-dialytic periods rather than during the 68-hour (approximately) inter-dialytic period.

Potential participants will be excluded if there is any serum potassium value of ≥ 6.5 mEq/L within 3 months prior to the Baseline/Randomization visit or if there is any serum potassium value ≥ 6 mEq/L within 2 weeks prior to the Baseline/Randomization visit. It is required that there be at least one serum potassium value obtained within 2 weeks prior to Baseline. The potassium measurement can be obtained either through routine clinical testing or as a research test. Participants who do not meet eligibility can be rescreened one additional time.

If the participant has agreed to participate in the heart rhythm monitoring sub-study, the first monitoring will be performed between the screening and baseline/randomization visits. The participant will wear the Medtronic SEEQ heart monitor for 7 consecutive days. Participants will receive the monitor kit from the research team and will return the kit after the monitoring period.

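### The model for incidence of potassium above 6.5 mEq/L omits the compulsory pre-randomization potassium; adding it would gain roughly 0 to 9 points of power, depending on a correlation the documents do not give

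*Combined protocol and SAP*

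**What the plan says.** Section 3.2.1 lists "The incidence of serum potassium >6.5 mEq/L" first among the primary safety endpoints. Section 7.4.1 gives the analysis: "Differences in incidence and incidence-rate will be assessed using logistic regression or Poisson regression with factors for assigned treatment and the stratification variable". Sections 5.3 and 7.2 name the stratification factors as clinical center, dialysis vintage and ACEI/ARB use. Section 5.3 justifies the last two because they "increase the likelihood of hyperkalemia through loss of residual renal function and drug effects, respectively". Potassium is not among them.

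Entry potassium is nevertheless always available. Section 6.2 states: "It is required that there be at least one serum potassium value obtained within 2 weeks prior to Baseline". Values of 6.0 mEq/L or more in that window exclude the patient.

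Section 7.4.1 does provide for baseline covariates in the mixed model for E' and, with and without, in the mixed model for serial potassium. It does not name those covariates, and it makes no such provision for incidence. For serious hyperkalemia it names a chi-square or Fisher's exact test.

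On size, Section 7.1 says "For the safety endpoint of hyperkalemia incidence, we assumed a 5% incidence in the placebo arm" and "this design provides 80% power to detect an average incidence of 22% across the 3 SPL dose arms", with "50 patients for the placebo arm and 25 per SPL dose x 3 active treatment arms".

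**The concern.** Vintage and ACEI/ARB use enter the model because they are indirect markers of hyperkalemia risk. Pre-randomization potassium is the outcome variable itself, measured earlier, and costs nothing further to collect. Leaving it out has two possible consequences. The comparison on a sparse primary endpoint may have less power than the data allow. And dose-arm contrasts, which Section 7.3 counts among the primary questions, carry any chance difference in baseline potassium between an arm of 25 and the placebo arm of 50.

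**Working it through.** **1. The plan's own power figure.** Inputs from Section 7.1: p0 = 0.05 (n = 50), p1 = 0.22 (n = 75, the three SPL arms pooled). Two-sided alpha of 0.05 is assumed, since Section 7.4.1 gives P < 0.05 without sidedness. The hyperkalemia sentence gives no threshold; the endpoint is taken to be potassium above 6.5 mEq/L.

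- Pooled normal formula: overall rate (2.5 + 16.5)/125 = 0.152. Null SE = √[0.152 × 0.848 × (1/50 + 1/75)] = 0.0655. Alternative SE = √[0.05 × 0.95/50 + 0.22 × 0.78/75] = 0.0569. Power = Φ[(0.17 − 1.96 × 0.0655)/0.0569] = Φ(0.73) = 76.7%.
- Exact enumeration of the uncorrected chi-square test at 50 v 75: 80.6%.
- Unpooled normal formula after 10% dropout (45 v 67.5): 80.9%.

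The stated 80% is therefore reproduced without any covariate. Section 7.1 assumes "a 10% dropout rate of study participants by the end of the study" for E' but does not say whether this applies to the hyperkalemia figure.

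**2. How sparse the endpoint is.** Expected events: 50 × 0.05 + 75 × 0.22 = 2.5 + 16.5 = 19. Chance of no placebo event: 0.95^50 = 7.7%.

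**3. Gain from adding entry potassium.** Potassium was simulated with a random intercept per person, total SD 0.7 mEq/L, entry value below 6.0, and 14 follow-up values (weeks 1 to 6, 8, 12, 16, 20, 24, 28, 32 and 36). It was calibrated to 5% and 22% with any value above 6.5. The SD is an assumption; one study in Section 1.3 reports 4.96 ± 0.72. The within-person correlation is also an assumption, so it is varied. The analysis was logistic, pooled SPL v placebo, with a likelihood-ratio test. Site, vintage and ACEI/ARB terms were in the model and were simulated as non-prognostic. Three sets of simulated trials gave these gains in power, in points:

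| Correlation | 1,500 trials per setting | 2,000 trials per setting | 1,500 trials per setting |
|---|---|---|---|
| 0.1 | not run | −0.3 | about 0 |
| 0.3 | +1.3 (82.4% to 83.7%) | +1.4 | about +1 |
| 0.5 | +2.7 (83.1% to 85.8%) | +4.0 | about +4 |
| 0.7 | +8.8 (82.3% to 91.1%) | +7.6 | about +6 |

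Monte Carlo error is about 1 point. Type I error was 5.6–5.7% without and 6.1–6.2% with potassium in the first set, 6.6% and 7.9% at correlation 0.7 in the second, and 5–7% and 5–7.5% in the third. At equal size, the second set's gains become about −2, 0, +4 and +7 points, so little or nothing remains at 0.3 or below.

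**4. Cross-check on another scale.** With a standard normal covariate and no strata, the likelihood-ratio gain is +1.1, +2.7, +5.2 and +7.0 points for odds ratios per SD of 1.5, 2, 3 and 4. With a score test it is −0.1, +1.4, +3.0 and +6.1. Unadjusted power is about 81–82% by likelihood ratio but only about 66–67% by Wald test. That difference of about 15 points between tests is larger than any gain from the covariate under the likelihood-ratio test.

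**5. Chance imbalance.** With an assumed mean of 4.9 and SD of 0.7, truncation at 6.0 leaves an SD of about 0.62. The standard error of the baseline difference between one SPL arm and placebo is 0.62 × √(1/25 + 1/50) = 0.15 mEq/L. For all SPL v placebo it is 0.62 × √(1/50 + 1/75) = 0.11 mEq/L. Section 7.1 treats 0.1 mEq/L in time-averaged potassium as a difference worth detecting.

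**The case against.** A reader might infer that the omission costs a definite several points of power. The documents do not support that. They give no correlation or odds ratio linking entry potassium to a later value above 6.5, and several of their features could make it a weak predictor:

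- Section 4.2 also excludes patients with potassium of 6.5 or more, or unscheduled dialysis for hyperkalemia, in the previous 3 months. This narrows the range further than the simulation did.
- Section 6.2 accepts any routine or research value and does not fix its timing relative to dialysis.
- A study summarized in Section 1.3 found peak potassium after a missed dialysis session, which is a post-randomization event.
- Section 6.9 alters study drug in response to potassium, a feedback that the simulation lacks.

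A reader might also infer that the planned comparison is wrong. It is not: randomization makes it valid, and the stated 80% is met without the covariate. Section 7.1 also disclaims formal critical regions for this pilot, which limits the weight of a power argument. Against that, Section 7.4.1 applies P < 0.05 to all analyses, and precision matters for estimation too.

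Section 7.4 says methods may be revised, and Section 7.4.1 compares baseline measures across groups and models serial potassium with covariates. None of this adjusts the incidence comparison, and a covariate chosen after the data are seen is worth less than one named in advance.

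Finally, a reader might extend the point to serious hyperkalemia and serious hypotension. Section 7.4.1 assigns serious hyperkalemia a chi-square or Fisher's exact test, and nothing in the documents supports adding systolic pressure to a serious-hypotension model that may be very sparse.

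**Conclusion.** The point stands as a missed, inexpensive gain in efficiency on a primary safety endpoint. It is not an error in the analysis. With the strata in the model and a likelihood-ratio test, the gain is roughly 0 to 9 points, and the upper end requires a within-person correlation near 0.7. These figures rest on the plan's 5% v 22%, the pooled 50 v 75 contrast, a logistic model, an SD of 0.7 mEq/L, 14 follow-up values and non-prognostic strata. Poisson models and separate dose-arm contrasts were not simulated. The correction of chance baseline imbalance is a second benefit that does not depend on significance testing, though it too is worth little if entry potassium predicts weakly.

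**What to change.** In Section 7.4.1, pre-specify the last serum potassium before randomization as a single linear covariate in the incidence models for potassium above 6.5 mEq/L (primary) and at or above 6.0 mEq/L (secondary). Exclude a sample drawn the day after randomization, which Section 6.3 allows for chemistries. Name the likelihood-ratio test. Report risk differences by arm standardized over the observed covariates, because the adjusted odds ratio is conditional on them. Keep the model without potassium as a sensitivity analysis. Leave the serious hyperkalemia and serious hypotension analyses as they are on this point.

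The cost is a few lines of SAP text and no new data. One more parameter is added to a model that already carries site, vintage, ACEI/ARB and treatment on about 19 expected events, and type I error may rise by about 1 point.
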